
In a secondary study to be done in collaboration with the NIDA IRP, participants will also undergo ambulatory monitoring of mood, behavior, and geolocation. The aim is to follow up on prior findings from the IRP that, unlike the general population, people in addiction recovery may experience work as a respite from stress.

2. Objectives

The project will have the following primary and secondary objectives:

Primary Objectives. Assess the effectiveness of the IPS Plus Abstinence-Contingent Wage Supplements in increasing competitive employment and preventing relapse to heroin and cocaine use.

Secondary Objective: Proximal and Distal Risk Factors. Assess the effectiveness of the IPS Plus Abstinence-Contingent Wage Supplements in reducing drug-related risk behaviors (proximal) and reducing family poverty (distal).

Secondary Objective: Post-Intervention Effects. Assess the effectiveness of the IPS Plus Abstinence-Contingent Wage Supplements in promoting long-term drug abstinence and employment and in reducing HIV risk.

Secondary Objective: Economic Analyses. Assess the costs, cost-effectiveness and cost-benefit of IPS Plus Abstinence-Contingent Wage Supplements relative to IPS Only.

Secondary Objective: Ambulatory Monitoring through Geographical Momentary Assessment (GMA). Replicate and extend prior findings that people in addiction recovery may experience work as a respite from stress rather than a stressor. Assess relationships among mood, drug craving, behavior, and activity space in Therapeutic Workplace participants compared to delayed work group, and across time in all participants.

3. Background

Drug addiction can be a chronic problem that can persist for many years and sometimes throughout a person's lifetime (Dennis et al., 2007; McLellan et al., 2000). Treatments can promote drug abstinence in some patients, but relapse is common after treatment (Knapp et al., 2007; Lancaster et al., 2006; Sees et al., 2000; Veilleux et al., 2010). Many individuals achieve periods of drug abstinence that last a year or more, but still relapse (Galai et al., 2003; Shah et al., 2006). The development of enduring solutions to sustain abstinence over many years is perhaps the greatest challenge facing the substance abuse treatment research community. This project seeks to develop a long-term treatment to address the chronic relapsing nature of drug addiction.

Treating Injection Heroin and Cocaine Use in Low-Income, Unemployed Adults

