b. Blinding, including justification for blinding or not blinding the trial, if applicable.

NA

c. Justification of why participants will not receive routine care or will have current therapy stopped.

NA

d. Justification for inclusion of a placebo or non-treatment group.

NA

e. Definition of treatment failure or participant removal criteria.

Participants will be removed from the study if they threaten the safety of CLH staff or other research participants, or of any other persons on the Johns Hopkins Bayview Campus.

f. Description of what happens to participants receiving therapy when study ends or if a participant's participation in the study ends prematurely.

Throughout the study, participants will be given referrals to services they might need (e.g., drug counseling, housing, medical, or employment services).

5. Inclusion/Exclusion Criteria

Inclusion criteria: a) ≥ 18 yrs old; b) unemployed; c) provide an opioid-positive (methadone, buprenorphine, or morphine) urine sample at intake; e) in methadone or buprenorphine treatment or meet DSM criteria for heroin dependence; and g) express interest in obtaining competitive employment.

Exclusion criteria: a) report current suicidal/homicidal ideation; b) have a severe psychiatric disorder.

6. Drugs/ Substances/ Devices

a. The rationale for choosing the drug and dose or for choosing the device to be used.

NA

b. Justification and safety information if FDA approved drugs will be administered for non-FDA approved indications or if doses or routes of administration or participant populations are changed.

NA

c. Justification and safety information if non-FDA approved drugs without an IND will be administered.

NA

7. Study Statistics

We will compare the *IPS* Plus Abstinence-Contingent Wage Supplement and *IPS* Only participants on primary, secondary and economic measures. Each measure is associated with a *Specific Aim*.

a. Primary outcome variable.

Specific Aim. Assess the effectiveness of the *IPS* Plus Abstinence-Contingent Wage Supplements in preventing relapse to heroin and cocaine. We will assess rate of urine samples negative for opiates and cocaine at the 12 monthly assessments during the year after random assignment (Y/N at each assessment).

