Specific Aim. Assess the effectiveness of the *IPS* Plus Abstinence-Contingent Wage Supplements in promoting employment. We will assess rate that participants report being employed at the 12 monthly assessments during the year after random assignment (Y/N at each assessment).

b. Secondary outcome variables.

Specific Aim. Assess the effectiveness of the *IPS* Plus Abstinence-Contingent Wage Supplements in reducing injection drug use. We will assess the rate that participants report injecting drugs in the past 30 days at the 12 monthly assessments in the year after random assignment (Y/N at each assessment).

Specific Aim. Assess the effectiveness of the *IPS* Plus Abstinence-Contingent Wage Supplements in reducing drug-related HIV risk behaviors. We will assess the rate that participants report sharing injection equipment (needles/syringes without disinfecting, cookers/cottons/rinse water, or drug solution) or trading unprotected sex for drugs or money in the past 30 days at the 12 monthly assessment during the year after random assignment (Y/N at each assessment). If the *IPS* Plus Abstinence-Contingent Wage Supplements reduces cocaine and opiate use, it should reduce these risk behaviors.

Specific Aim. Assess the effectiveness of the *IPS* Plus Abstinence-Contingent Wage Supplements in reducing family poverty. We will assess whether family income is at or below the federal poverty level at the 12 monthly assessments during the year after random assignment (Y/N at each assessment) with and without wage supplement earnings. *IPS* Plus Abstinence-Contingent Wage Supplements should reduce poverty.

Specific Aim. Assess the effectiveness of the *IPS* Plus Abstinence-Contingent Wage Supplements in promoting long-term drug abstinence and employment and in reducing HIV risk. We will compare the groups on all measures of heroin and cocaine use, employment, and HIV risk behaviors at 3-, 6-, 9- and 12-month follow-up assessment time points after *IPS* and abstinence-contingent wage supplements have ended.

Specific Aim. *Assess the costs of treatment for IPS Only and IPS Plus Abstinence-Contingent Wage Supplements.* We will assess the total cost per participant of both study interventions. We expect that treatment costs for IPS Plus Abstinence-Contingent Wage Supplements will be higher per person relative to the IPS Only due to the wage supplements and because we expect that IPS Plus Abstinence-Wage Supplement participants will have greater treatment engagement.

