
Specific Aim. *Assess the cost-effectiveness of IPS Plus Abstinence-Contingent Wage Supplements.* Separate cost-effectiveness analyses will be conducted for the outcomes of substance use, employment, and drug-related HIV risk behavior. We will assess incremental cost-effectiveness ratio (ICER) by dividing the difference in costs of two interventions by the difference in the effects of the two interventions. The estimated ICER can be interpreted as dollars spent per unit of desired outcomes gained. We expect that IPS Plus Abstinence-Contingent Wage Supplements will yield better ICERs for all three measures.

[figure not shown]
Specific Aim. *Assess the cost-benefit of IPS Plus Abstinence-Contingent Wage Supplements.* We will perform a Cost-Benefit Analysis (CBA) to examine the monetized benefits relative to costs for the two intervention conditions. The economic outcomes are employment, crime, and health care utilization. We expect that IPS plus Wage Supplement will yield greater economic benefits in criminal activity, health care utilization, and employment in the 24-month post enrollment time period relative to its costs than the IPS only condition.

Specific Aim. *Geographical Momentary Assessment.* We will assess collect the four types of ambulatory entries described above (randomly prompted entries and three types of event-related entries), along with time-stamped latitude and longitude data from the smartphone's GPS unit. In some analyses, we will examine the latitude and longitude data in terms of objective information about social disorder in the neighborhoods where they were collected, as we have done in our published work (Epstein et al., 2014).

- c. Statistical plan including sample size justification and interim data analysis.

Power Analysis

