The primary outcome measures will be analyzed with a longitudinal logistic regression model using GEE (Diggle et al., 2002). We used Liu and Liang (1997) to determine the total N required to detect differences between groups with 80% power. The adjacent figure shows the total number of participants (N) that would be required to detect a difference of 15% between the IPS Only and the IPS Plus Abstinent-Contingent Wage Supplement with the 12 monthly assessments. The adjacent figure shows possible percentages for the IPS Only group because that value affects the sample size required. Fifteen percent is smaller than any difference in any Therapeutic Workplace study in which we promoted cocaine abstinence in methadone patients. This difference is also smaller than any difference between Control and IPS groups in the percentage of participants that become employed. Based on this, we need a maximum of 120 participants (horizontal dashed line) to detect a difference between the IPS Only and the IPS Plus Abstinent-Contingent Wage Supplement groups of 15% or more on each primary outcome.

Statistical Analyses

Main analysis. All measures assessed repeatedly over time will be analyzed with a longitudinal logistic regression model. Within-person correlated outcomes will be handled using generalized estimating equations (GEE; Zeger et al., 1988). Measures assessed once will be analyzed using logistic regression. The magnitude of effect for both logistic regression and GEE will be expressed using odds ratios with 95% CI. Analyses will include all randomized participants as intent-to-treat, and will be adjusted for pre-specified covariates used for stratification (Pocock et al., 2002). Tests will be two-sided and p-values <.05 will be considered significant.

Moderator analyses. We will conduct analyses to identify variables that moderate the outcomes of our two primary outcome measures, employment and drug (opiates and cocaine) abstinence. We will examine differences in efficacy as a function of two variables assessed prior to random assignment by including interaction terms in our regression models: 1) Percentage of urine samples negative for opiates and cocaine at the three monthly urine samples collected prior to random assignment. 2) Completed high

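### Two primary outcomes are each tested at two-sided .05 with no rule across them, and the named effect measure is an odds ratio although the trial is sized on a 15-point difference in rates

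*Combined protocol and SAP*

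**What the plan says.** Section 2 puts both outcomes into one primary objective: "increasing competitive employment and preventing relapse to heroin and cocaine use". Section 7a then gives each its own Specific Aim. For abstinence: "We will assess rate of urine samples negative for opiates and cocaine at the 12 monthly assessments". For employment: "We will assess rate that participants report being employed at the 12 monthly assessments". Both are yes/no at each monthly visit in the year after randomization. The Moderator analyses paragraph of 7c confirms their status, referring to "our two primary outcome measures, employment and drug (opiates and cocaine) abstinence".

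The Main analysis paragraph of 7c fits longitudinal logistic models by GEE, adjusted for the stratification covariates. On significance it says: "Tests will be two-sided and p-values <.05 will be considered significant". On size of effect it says: "The magnitude of effect for both logistic regression and GEE will be expressed using odds ratios with 95% CI".

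The Power Analysis works on a different scale. It gives a maximum of 120 participants, at 80% power, to detect a difference between the two "groups of 15% or more on each primary outcome".

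The document gives no testing order, no division of alpha and no statement of whether one or both outcomes must succeed. It plans no rate difference with a confidence interval for either primary outcome.

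**The concern.** Two things are left open at the point where the trial will be interpreted.

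First, with two primary tests at the full .05 and no stated rule, a report could treat significance on either outcome as evidence that the intervention works. That use gives two chances of a false positive. If both outcomes are meant to be needed, alpha is not inflated, but the relevant power is then the power for both, which the plan does not quote.

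Second, the design question is whether the groups differ by 15 points. How many points an odds ratio represents depends on the IPS Only rate, and that rate may differ between abstinence and employment. A reader given an odds ratio and its interval cannot read off whether the design difference was reached, or whether a null result excludes it.

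**Working it through.** **Inputs from the documents.** Two primary outcomes; two-sided .05; 80% power; a 15% difference; 12 monthly assessments; N=120. I read 15% as percentage points; the prior study in section 3 is described the same way (79.3% against 50.7%, or 28.6 points).

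**Assumed.** Allocation 1:1 and two-sided .05 in the power calculation. The IPS Only rates and within-person correlation r are not in the readable text because the power figure is not shown.

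**1. The plan's own figure.** For repeated binary data with exchangeable correlation,

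N = 2(1.960+0.842)² × [p1q1+p2q2] / d² × (1+11r)/12.

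At the least favourable rates, 42.5% against 57.5%, p1q1+p2q2 = 0.489. N is 91 at r=0.2, 122 at r=0.3 and 185 at r=0.5; r=0.293 returns exactly 120. So 120 is plausible, but cannot be confirmed.

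**2. False positives when both nulls are true and either win counts.**
- Independent tests: 1 − 0.95² = 9.75%.
- Bivariate normal: 9.5% at test correlation 0.3, 9.1% at 0.5, 7.8% at 0.8.
- Upper bound: 0.05 + 0.05 = 10%.

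**3. Power under Holm, starting from exactly 80% per outcome.** Here d/SE = 2.802, and power at .025 is Φ(2.802 − 2.241) = 0.712. An outcome is rejected if its own p-value is below .025, or if it is below .05 and the other is below .025.
- Both effects 15 points, independent tests: 0.712 + (0.800 − 0.712) × 0.712 = 0.775. Simulation at test correlation 0.5 gives 0.765.
- Other outcome null: 0.712 + 0.088 × 0.025 = 0.714.

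**4. Power if both must succeed at .05.** Independent tests: 0.80² = 0.64. At test correlation 0.5: 0.687. These apply when each outcome has exactly 80%. Because 120 is a maximum over IPS Only rates, power is higher at other rates. For example, with r=0.293 and a 20% employment rate, SE² = (0.16+0.2275)/60 × 0.352 = 0.00227, d/SE = 3.15 and power is 88%. Joint power with abstinence at 42.5% is then 0.88 × 0.80, about 71% for independent tests.

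**5. Odds ratio against points.**

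| IPS Only rate | Odds ratio for 15 points | Points if the odds ratio is 1.83 |
|---|---|---|
| 42.5% | 1.83 | 15.0 |
| 20% | 2.15 | 11.4 |
| 10% | 3.00 | 6.9 |

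First row: (0.575/0.425)/(0.425/0.575) = 1.83. Last row, third column: odds 0.111 × 1.83 = 0.203, a rate of 16.9%, less 10%.

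**6. What a rate difference would show.** At an observed zero difference, the 95% half-width is 1.96 × √(2pq/60 × (1+11r)/12). With r=0.293 it is 8.5 points at p=20% and 10.6 at p=50%. It runs from 7.4 (r=0.2, p=20%) to 13.2 (r=0.5, p=50%). Under these assumptions such a result would exclude 15 points, though not every smaller gain.

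**The case against.** The strongest reply is that section 7 ties each measure to its own Specific Aim and sizes the trial for each outcome separately. On that view these are two questions, each properly answered at .05, and no overall claim is defined that could be inflated. This stands in part. A reader might infer that the plan simply runs a 10% error rate. The documents do not support that: the figure applies only if a win on either outcome is used to claim effectiveness. But the plan does not say the outcomes will be interpreted separately, and section 2 places them under a single primary objective.

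A reader might also infer that the 80% overstates the chance of success, or that N=120 is too small. Neither follows. The plan claims 80% for each outcome and never as power for both. The 64% is a low end, since 120 is a maximum.

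On the odds ratio, the reply is that both outcomes are defined as rates and nothing forbids printing group rates. That is fair. Even so, group rates alone give no interval for their difference. A reader might go further and infer that the cost-effectiveness analysis lacks a difference in effects. It does not: section 7b forms its ratio "by dividing the difference in costs of two interventions by the difference in the effects of the two interventions", and Economic Analyses in 7c gives it its own effectiveness measures and bootstrap intervals.

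Finally, the Power Analysis supports 15 points on employment with differences between Control and IPS, whereas here both arms are offered IPS. A reader might infer that the employment target is wrong. The text does not show that, and rewording the sentence would change no result.

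**Conclusion.** The point holds as an inexpensive improvement, not as an error in the sample size. If either outcome can carry an effectiveness claim, the family-wise error is about 9–10% for test correlations up to 0.5, against a nominal 5%. That figure needs neither the missing figure nor an IPS Only rate. The power figures under Holm and under a both-must-succeed rule rest on each outcome having exactly 80% at a 15-point effect.

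The odds ratio alone does not settle whether 15 points was reached or excluded; 1.83 spans 6.9 to 15.0 points over IPS Only rates of 10% to 42.5%. Those rates are illustrative, and the conversion applies the odds ratio to one IPS Only rate, ignoring covariate adjustment. The interval widths in step 6 also rest on the assumed r.

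**What to change.** Keep N=120 and make two changes to the Main analysis paragraph of 7c.

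1. Test the two primary outcomes with Holm at an overall two-sided .05. This holds the family-wise error at or below 5% whatever the correlation between the tests. The cost is power per outcome: from 80% to about 77% if both effects are 15 points, and to about 71% if the other outcome has no effect. If the sponsor instead intends that both must succeed, leave each at .05, say so, and quote joint power: at least about 64% (independent tests) to 69% (test correlation 0.5) when each outcome has 80%, and higher where the IPS Only rate needs fewer than 120 participants.
2. For each primary outcome, report beside the odds ratio the difference in monthly rates from the same GEE model, standardized over the stratification covariates and averaged over the 12 assessments, with its 95% CI. Interpret that interval against 15 points, including when the result is null.

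Neither change adds participants or visits. Timing matters: the COVID-19 procedures in section 4 refer to remaining assessments, so the trial is well under way. The testing rule should be fixed before group comparisons are seen, or labelled post hoc if they already have been. The rate difference is useful either way.

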Abstinence-contingent wage supplements. Participants in this group will receive abstinence-contingent wage supplements. Abstinence-contingent wage supplements should have three main effects: 1) promote engagement in IPS, 2) promote competitive employment, and 3) maintain drug abstinence. Before obtaining competitive employment, participants will be able to earn wage supplements for attending IPS sessions each week, and for completing specific tasks prescribed by IPS including developing a worker profile, applying for appropriate jobs, and completing job interviews. This incentive system will be designed to allow participants to earn about \$200 per week and will include methods to verify the completion of the target behaviors. If needed, we may offer bonus incentives to increase some job-seeking behaviors (e.g., completing job applications). We may also evaluate the effectiveness of those bonus incentives, for example, by applying and withdrawing them to see if those bonus incentives are needed to promote the job seeking behaviors. Once a participant becomes employed, participants will be able to earn up to \$8 per hour for every hour worked in a competitive job up to 40 hours per week verified by pay stubs. To maintain long-term abstinence from opiates and cocaine, participants will be required to provide urine samples to earn the maximum in wage supplements.

Abstinence monitoring. After random assignment, a drug testing schedule will be established for each participant and this schedule will be shared with ASAP®. Participants will be required to call our wage supplement staff every Monday, Wednesday and Friday morning to find out if they are required to report to our urinalysis laboratory or a participating SAMSHA-approved urine collection facility to provide a urine sample. Participants will be given a list of the participating collection facilities in the Baltimore area. One of the facilities is open 24 hours per day, 7 days per week; one is open from 7 am to 7 pm every weekday; one is open from 8 am to 8 pm every weekday; and one is open 8 am to 5 pm every weekday. If a participant is out of town (e.g., on vacation), the participant can contact our laboratory staff, who will identify the nearest collection facility for that participant by conducting a geo-access match using the zip codes and physical address of the participant's location. The results of testing will be available to the wage supplement staff on a secure website.

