school or obtained a GED (Y/N)? We expect that opiate and cocaine use prior to random assignment will be associated with higher rates of drug use and lower rates of employment during the year after random assignment. We expect that high school completion or obtaining a GED will be associated with higher rates of employment. We also expect that the effect of IPS Plus Abstinence-Contingent Wage Supplements will be affected by these variables.

We will conduct similar analyses to identify variables that moderate outcomes on employment and drug use during the follow-up year after IPS and abstinence-contingent wage supplements have ended. We will examine differences in outcomes during the follow-up year as a function of two variables assessed at the end of the intervention evaluation period by including interaction terms in our regression models: 1) Percentage of urine samples positive for cocaine or opiates at the last three monthly urine samples collected under the study interventions; 2) Highest hourly wage that each participant earned during the year after random assignment. We expect that opiate and cocaine use during the last 3 months under the study interventions will be associated with higher rates of drug use and lower rates of employment during the follow-up year. We expect that the highest wage achieved during the year that the study interventions were in effect will be associated with higher rates of employment and lower rates of drug use during the follow-up year. We also expect that IPS Plus Abstinence-Contingent Wage Supplements effects will be affected by these variables.

Missing data. We expect to collect >90% of assessments (see below). Our primary approach to handle missing data will be to impute all missing values as the adverse outcome (e.g., cocaine positive). Model parameter estimates from this approach will be compared to a method without imputation. If these methods yield differing results, conclusions will need to be tentative. To investigate sensitivity to missing values, participants with and without missing values will be compared by covariates and treatment assignment.

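### Follow-up-year moderator models interact treatment with two post-randomisation variables that the intervention can itself change

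*Combined protocol and SAP*

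**What the plan says.** Section 7c, Moderator analyses, describes two sets of models.

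- **Intervention year.** The moderators are "two variables assessed prior to random assignment by including interaction terms in our regression models": the percentage of pre-randomisation monthly urines negative for opiates and cocaine, and high school or GED completion. The paragraph ends: "We also expect that the effect of IPS Plus Abstinence-Contingent Wage Supplements will be affected by these variables".
- **Follow-up year.** The paragraph opens: "We will conduct similar analyses to identify variables that moderate outcomes on employment and drug use during the follow-up year". Outcomes are examined "as a function of two variables assessed at the end of the intervention evaluation period by including interaction terms". The two variables are the percentage of the last three on-intervention monthly urines positive for cocaine or opiates, and "Highest hourly wage that each participant earned during the year after random assignment". Each is expected to predict later outcomes, and the paragraph closes: "We also expect that IPS Plus Abstinence-Contingent Wage Supplements effects will be affected by these variables".

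Section 4 says what the supplements are for: "Abstinence-contingent wage supplements should have three main effects: 1) promote engagement in IPS, 2) promote competitive employment, and 3) maintain drug abstinence". Adjustment is limited to the stratification factors (Section 7c, Main analysis; Section 4, Random Assignment). For missing data: "Our primary approach to handle missing data will be to impute all missing values as the adverse outcome". Nothing labels the follow-up models as descriptive or plans a mediation or principal-stratum method.

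**The concern.** The year-1 moderators are fixed before randomisation, so a treatment-by-moderator term there compares like with like. The follow-up moderators are not. Late on-intervention urine status is the last part of a primary outcome and a direct target of the intervention. Highest wage may change because the supplements promote employment.

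Two problems follow if some underlying trait, such as severity, drives both the moderator and the follow-up outcome and is not fully captured by the dichotomised stratification factors.

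1. **Treatment effect at a given moderator value.** A participant who finished abstinent while paid for abstinence is, on average, more severely affected than one who finished abstinent without payment. Comparing them makes the intervention look harmful even if it has no lasting effect.
2. **The interaction itself.** If the intervention moves the urine variable more in some participants than in others, the severity gap between arms differs along the moderator, and the interaction is biased too. The plan expects unequal response: it says the year-1 effect will vary with pre-randomisation drug use, without giving a direction.

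The analysis is presumably meant to show whose gains last once supplements stop. It could report that lasting benefit depends on how participants finished, or that supplements harm people at a given status, when neither is true.

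**Working it through.** **The plan's own figure.** The plan gives none for these models. Its total of 120 enters only as the trial size. That total cannot be reproduced from stated inputs, because no within-person correlation ρ is given. With the worst-case single-assessment size of 170.5 per arm for a 15-point difference, N = 2 × 170.5 × (1 + 11ρ)/12, which is 120 at ρ ≈ 0.293. Nothing below depends on this.

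**Inputs from the documents.** 60 per arm; four follow-up visits; two-sided 5% tests; a 15-point design difference (Section 7c, Power Analysis); 79.3% − 50.7% = 28.6 points from the earlier employment study (Section 3), so 49.3% versus 20.7% positive.

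**Assumed inputs.** Cocaine and opiate severity are normal with SD 0.5, 1.0 or 1.5 logits and correlation 0.5; 50% of follow-up samples are positive; there is no true follow-up effect. For the 15-point case, late samples are 50% versus 35% positive.

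**Model.** logit P(positive at follow-up) = β₀ + β_A·arm + β_M·M + β_AM·arm·M + stratification factors, fitted by independence GEE with sandwich errors, where M is the share of the last three samples positive. The treatment odds ratio at M = m is exp(β_A + β_AM·m); above 1 is apparent harm. There were 4,000 trials per setting, so the Monte Carlo error of a 5% rate is √(0.05 × 0.95/4000) = 0.34 points.

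**Results** for SD 0.5/1.0/1.5 (median odds ratios):

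| Effect on late urines | OR at mean M (false positives) | Interaction OR (false positives) |
|---|---|---|
| None | (6.2/6.0/5.9%) | (6.4/5.9/5.9%) |
| Equal logit shift, 15 points | 1.08/1.22/1.35 (7.4/14.5/23.1%) | (6.8/5.8/6.5%) |
| Equal logit shift, 28.6 points | 1.15/1.47/1.81 (11.1/34.2/56.1%) | (6.4/5.9/7.5%) |
| Only above-average severity responds, 15 points | | 0.55/0.55/0.63 (15.4/14.3/10.1%) |
| Only above-average severity responds, 28.6 points | | 0.27/0.17/0.22 (48.8/61.4/45.0%) |
| Only below-average severity responds, 15 points | | 1.36/1.17/not reachable (9.8/7.1%) |

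- In the fifth row the treatment OR is 1.52/2.03/2.23 at 0% positive and 0.41/0.36/0.49 at 100% positive. As a check, 1.52 × 0.27 = 0.41 and 2.23 × 0.22 = 0.49.
- Response graded with severity, in either direction, gives false interactions in 6.4–9.2% at 15 points and 7.3–18.0% at 28.6.
- With 10% of samples missing and set to positive in both M and the outcome (SD 1.0–1.5), the equal-shift OR is 1.15–1.31 (10–20%) at 15 points and 1.29–1.70 (20–50%) at 28.6. The interaction when only above-average severity responds falls to 9–14% and 29–49%. The bias shrinks but remains.
- Over all 53 settings the OR at the mean moderator exceeded 1 in 52; the exception was 0.96.
- Without M in the model: OR 0.99–1.00, rejection 5.4–6.1%. With the pre-randomisation urine percentage as moderator: false interactions 5.1–6.3%.

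**A differently built check.** This used one million participants and a latent trait favouring abstinence, with abstinence as the outcome, so OR below 1 is apparent harm. Treatment lowers late positives from 50% to 33% and has no direct follow-up effect. The unadjusted OR is 1.00, but the OR is 0.67, 0.64, 0.61 and 0.58 at 0, 33, 67 and 100% positive. The cause is visible: among those 0% positive, the mean trait is 0.71 in treated participants and 1.01 in controls. Unequal response gives an interaction OR of 0.58 or 2.84, depending on who responds. If the trait does not affect the outcome, all ORs are about 1.00, so a common cause is necessary.

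**Wage.** With never-worked coded 0 and ever-employed 15 points apart (assumed), the treatment OR for follow-up employment is 0.84–0.90 (7.6–9.9%) and false interactions 6.1–6.9%. The effect is much weaker. If the $8 supplement were counted in the wage, the second model gave OR 0.71 at $11 even with no effect on employment.

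**The case against.** The follow-up paragraph is largely prognostic. It speaks of differences in outcomes where the year-1 text speaks of efficacy, and its two specific expectations are associations that need no causal reading. The plan does not promise treatment effects at chosen moderator values, yet the most striking equal-shift figures concern exactly those. For the interaction, which is planned, an equal shift gives 6–8% against about 6% with none, and at the 15-point design difference even all-or-none response reaches only 7–15%. The 45–61% figures need both all-or-none response and the 28.6-point difference, which is cocaine-only and comes from hired participants who had already initiated abstinence. The direction is not fixed either: at 100% positive the OR can fall well below 1. As pure description, the model estimates what it is asked.

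Most of this stands as a limit on size. It does not remove the point. The models are introduced as a search for moderators, parallel to year 1, with interaction terms, and the closing sentence says the intervention's effects will depend on these variables. That is a claim about effect modification, and no descriptive label is attached. The fitted model also yields conditional treatment effects whether or not they were promised.

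**Conclusion.** The concern holds. Both follow-up-year moderators are post-randomisation, one is a direct target of the intervention, and the planned interaction is with treatment. Conditional treatment effects can be biased, usually toward apparent harm, and the interaction can be biased in either direction when response is unequal.

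The size is uncertain. It ranges from negligible (severity SD 0.5, equal shift, 15 points: 7.4% false treatment effects) to large (false interactions in 45–61% of trials when only more severe participants respond and the difference is 28.6 points). Severity spread and response pattern are assumptions. Wage supplements had not been systematically evaluated (Section 3), so neither 15 nor 28.6 points is a known bound. The bias requires persistent severity linking late and follow-up drug use, which fits the plan's own reason for stratifying on prior drug use. The wage moderator matters much less.

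This is a secondary analysis. The primary analyses and the follow-up group comparison in Section 7b do not use these variables and remain valid. The wording should be changed, but no main conclusion is at risk.

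**What to change.** Amend the follow-up-year paragraph of Section 7c as follows:

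- For effect modification in the follow-up year, use the two pre-randomisation moderators already specified for year 1.
- Keep late drug use and highest wage as prognostic associations, for example within arm. State that neither their interactions with treatment nor treatment effects at given values will be read as moderation. Differences between within-arm slopes fall under the same caveat, since they are the same interaction. Alternatively, present these variables in a mediation or principal-stratum analysis with its assumptions written down.
- Take follow-up treatment effects only from the group comparison at 3, 6, 9 and 12 months (Section 7b).
- State how highest hourly wage is coded for participants who never worked, and whether the supplement counts. These are minor, separate gaps.

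The cost is SAP wording only: no new data or visits. The loss is that whether end-of-intervention status modifies lasting benefit will be answered only descriptively, or under stated assumptions.
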